#### 7.4.3. Maintenance Period

Subjects will remain on the dose of XP-8121 used at the end of the Titration Period.

If, during Maintenance Period, biochemical hyperthyroidism is present, as evidenced by elevated trough fT4 and/or low TSH, the Investigator may reduce the weekly dose of XP-8121 SC by one dose level (ie, 25% of the target dose) and maintain the lowered dose throughout the remainder of the study as tolerated. If multiple signs/symptoms of thyroid excess are present without definitive biochemical evidence of hyperthyroidism, the Investigator should confer with the Medical Monitor. If the Investigator and Medical Monitor agree to a XP-8121 dose reduction, the dose should be reduced by one dose level and held at the lowered dose for the remainder of the study, as tolerated.

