## 8. SELECTION AND WITHDRAWAL OF SUBJECTS

### 8.1. Subject Inclusion Criteria

To be eligible, a subject must meet all the following inclusion criteria:

1. Provide written informed consent.
2. Male or female between the ages of 18 and 65 years (inclusive) at Screening, with chronic hypothyroidism and on a stable dose of oral levothyroxine (Synthroid or an FDA-approved generic equivalent to Synthroid) or, if in the PK substudy, Synthroid only for at least 3 months.
3. TSH within the normal range at Screening (study reference range: 0.47 to 4.68 µIU/mL) and at least 3 months prior to Screening (documented by local laboratory).
4. Free T4 within the normal range at Screening (study reference range: 0.78 to 1.42 ng/dL).
5. Women of childbearing potential (WOCBP) must have a negative urine pregnancy test at Screening and agree to use medically accepted contraception (except for contraceptives containing estrogen for PK substudy subjects only), or abstinence throughout the study.
6. Body Mass Index (BMI) 18 to 40 kg/m^2 at Screening.
7. Average triplicate blood pressure (BP) reading for systolic BP >90 mmHg and <150 mmHg and diastolic BP >40 mmHg and <100 mmHg at Screening.
8. Average triplicate resting heart rate/pulse >40 beats per minute (bpm) or <100 bpm at Screening.
9. Agrees to return to the CRU for all study visits, and if a part of the substudy PK group, remain at the CRU to comply with all required study procedures.

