### 13.1. Sample Size Determination

Assuming a between-subject coefficient of variation of 0.5 and a within-subject, between measurements correlation of 0.5, a sample size of 38 subjects will have 80% power to reject the null hypothesis that the dose conversion factor is less than 3.2X or more than 5X, in favor of the alternative hypothesis that the dose conversion factor is between 3.2X and 5X (in other words, within 80% and 125% of the proposed 4X conversion factor derived from PPK modeling). For the exploratory endpoint of TSQM-9, assuming a SD of differences of 20, a sample size of 34 subjects will have 80% power to detect a difference of 10 in means (domain scores range from 0 to 100) with a 5% two-sided significance level ( $\alpha=0.05$ ). Taking into consideration study non-completers and non-normalizers of TSH at study end, a total of 44 subjects will be enrolled.

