### 13.4. Analysis Populations

**Safety Population:** All subjects who receive at least 1 dose of XP-8121.

**Completer Population:** All subjects who complete the Maintenance Period and exhibit normalized TSH throughout the Maintenance Period while on a stable dose for approximately 6 weeks.

**PK Population:** All safety population subjects who participate in the PK substudy, who do not have any major protocol deviations affecting the PK endpoints and for whom a sufficient number of samples is available to determine at least one PK parameter.

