#### 13.5.1.1. Analysis of Primary Endpoint (Dose Conversion Factor)

The final dose conversion factor will be assessed by comparing the ln-transformed final XP-8121 SC dose (in  $\mu\text{g}$ ) that maintains normalized TSH throughout the Maintenance Period to the ln-transformed daily oral levothyroxine dose (in  $\mu\text{g}$ ) the subject was taking before the study, using a linear mixed effects model with treatment as fixed effects, and subject as random effect. Geometric LSMEs, geometric mean ratios, and 90% CIs will be presented. This endpoint will be analyzed using the Completer population for subjects with primary hypothyroidism only. Additional sensitivity analyses that include subjects with secondary/tertiary hypothyroidism, subjects with dose adjustment, and/or subjects that maintain normal free T4 may be conducted. The details of the sensitivity analyses will be described in the SAP.

Analysis of safety endpoints will be described in Section 13.7.

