### 13.5.2. Secondary Endpoints

The secondary endpoints of the study are as follows:

- Proportion of subjects enrolled with normalized TSH throughout the Maintenance Period
- Proportion of subjects enrolled with normalized TSH at the end of Maintenance Period
- Blood thyroid hormone concentrations (total thyroxine, fT4 and TSH) following the first dose of XP-8121 and after titration (ie, during the Titration and Maintenance Periods)

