4.4 Sample Size Considerations

Assuming a between-subject coefficient of variation of 0.5 and a within-subject, between-measurements correlation of 0.5, a sample size of 38 subjects will have 80% power to reject the null hypothesis that the dose conversion factor is less than 3.2X or more than 5X, in favor of the alternative hypothesis that the dose conversion factor is between 3.2X and 5X (in other words, within 80% and 125% of the proposed 4X conversion factor derived from Population PK modeling). For the exploratory endpoint of the treatment satisfaction questionnaire for medication (TSQM-9), assuming a SD of differences of 20, a sample size of 34 subjects will have 80% power to detect a difference of 10 in means (domain scores range from 0 to 100) with a 5% two-sided significance level ($\alpha=0.05$). Taking into consideration non-completers and non-normalizers of TSH at study end, a total of 44 subjects will be enrolled.

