7. ANALYSIS SETS

Analysis Set	Definition	Used for Analyses
Safety Population	All subjects who received at least one dose of XP-8121.	Disposition, Demographics, Medical History, Disease History, Concomitant Medications, Deviations, Safety Analyses, Tolerability endpoints Secondary endpoints, Exploratory endpoints (except PK related endpoints)
Completer Population	All subjects who completed the Maintenance Period and exhibit normalized TSH throughout the Maintenance Period while on a stable dose for approximately 6 weeks. Subjects with a reduced dose at any point during the Maintenance Period will not be included.	Dose Conversion Factor analysis, Sensitivity analysis of Change from Baseline of Blood Thyroid Hormone Concentrations Secondary Endpoint
PK Population	All safety population subjects who participated in the PK sub-study, who do not have any major protocol deviations affecting the PK endpoints and for whom a sufficient number of samples is available to determine at least one PK parameter.	PK analyses

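### Does the step from 38 to 44 subjects leave out exclusions that the primary analysis applies?

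*Protocol*

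**What the plan says.** Protocol 13.1 gives 80% power with 38 subjects for showing that the conversion factor lies between 3.2X and 5X. It assumes a between-subject CV of 0.5 and a correlation of 0.5. It then moves to enrolment: "Taking into consideration study non-completers and non-normalizers of TSH at study end, a total of 44 subjects will be enrolled". The Synopsis repeats this, and SAP 4.4 has almost the same sentence: "Taking into consideration non-completers and non-normalizers of TSH at study end, a total of 44 subjects will be enrolled". No rate is attached to either reason.

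The set that is analysed is defined elsewhere:

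- Protocol 13.4 requires Completers to finish Maintenance and to "exhibit normalized TSH throughout the Maintenance Period while on a stable dose for approximately 6 weeks".
- Protocol 13.5.1.1 adds a diagnosis condition: "This endpoint will be analyzed using the Completer population for subjects with primary hypothyroidism only".
- SAP 7 adds: "Subjects with a reduced dose at any point during the Maintenance Period will not be included".

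Eligibility is wider. Protocol 8.1 admits subjects "with chronic hypothyroidism and on a stable dose of oral levothyroxine", whatever the cause. Under Protocol 7.4.3, when there is biochemical hyperthyroidism in Maintenance, "the Investigator may reduce the weekly dose of XP-8121 SC by one dose level". Protocol 7.2.1 rules out replacing withdrawn subjects.

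**The concern.** The 38 have to be subjects in the primary analysis. The stated allowance names only non-completion and abnormal TSH at the end. Three other routes out of the set are not named:

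1. TSH out of range earlier in Maintenance but normal at the end.
2. A dose reduction in Maintenance.
3. Secondary or tertiary hypothyroidism.

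The plan itself treats the first as a separate matter. Protocol 13.5.2 lists "Proportion of subjects enrolled with normalized TSH throughout the Maintenance Period" as one secondary endpoint and normal TSH at the end of Maintenance as another. Anyone normal throughout is also normal at the end, so the first count cannot exceed the second.

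If 44 had been worked out from end-of-study losses alone, fewer than 38 subjects could qualify and power would fall below 80%. Protocol 5.5 makes the dose conversion target the basis for the hypothesis test and the sample size, and Protocol 13.5.3.1 gates the TSQM-9 tests on the primary result. A reader would therefore want to know what power 44 enrolled subjects deliver.

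**Working it through.** **Inputs.** From Protocol 13.1: CV 0.5, correlation 0.5, limits 3.2X and 5X around 4X (±ln 1.25 = ±0.2231 on the log scale), n = 38, enrolment 44. The power statement gives no alpha. The 90% interval in Protocol 13.5.1.1 implies two one-sided 5% tests, which I assume, together with a true factor of 4X.

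**Reproducing 38.** The log-scale variance is ln(1 + 0.5²) = 0.2231. The plan does not say on which scale the correlation applies, so there are two readings of the SD of the log ratio:

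- Log scale: √(2 × 0.2231 × (1 − 0.5)) = 0.472.
- Original scale: √(2 × (ln 1.25 − ln 1.125)) = 0.459.

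The normal approximation with 0.472 gives n = (0.472 × (1.645 + 1.282) / 0.2231)² ≈ 38.4, and power of 79.5% at 38. The exact paired test (n − 1 degrees of freedom) gives 0.805 at 38 with SD 0.459 and 0.775 with SD 0.472. The plan's figure stands.

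**The allowance.** 44 − 38 = 6, and 6/44 = 13.6%. So 38/44 = 86.4% of those enrolled must qualify.

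**Power by number qualifying (exact).**

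| Subjects in primary set | SD 0.459 | SD 0.472 |
|---|---|---|
| 38 | 0.805 | 0.775 |
| 36 | 0.776 | 0.743 |
| 34 | 0.742 | 0.707 |
| 30 | 0.660 | 0.622 |
| 26 | 0.556 | 0.515 |

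Each subject lost just below 38 costs about 1.5 to 2 points.

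**What would have to be assumed.** The documents give no qualifying rate. Treating the number who qualify as binomial with 44 enrolled, for assumed rates:

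| Assumed rate | Chance of at least 38 | Average power, SD 0.459 | Average power, SD 0.472 |
|---|---|---|---|
| 86.4% | 0.61 | 0.80 | 0.77 |
| 80% | 0.20 | 0.76 | 0.73 |
| 75% | 0.05 | 0.72 | 0.68 |
| 70% | 0.01 | 0.67 | 0.64 |

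**Effect of requiring normal TSH throughout.** TSH is drawn on Maintenance Days 1, 8, 15, 22 and 29. Suppose each value is in range with probability 0.95 (assumed). At the end visit 0.95 × 44 ≈ 42 are normal. Across all five visits:

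- Independent visits: 0.95⁵ × 44 = 34.
- Latent correlation 0.5: 0.817 × 44 ≈ 36.
- Latent correlation 0.9: 0.898 × 44 ≈ 40.

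The further loss is therefore 2 to 8. The upper end needs a subject's weekly TSH values on a fixed dose to be independent, which is implausible. SAP 6.2.3 makes the last value before the first Maintenance dose the period baseline. If that value is not counted, four visits remain and the independent case is 0.95⁴ × 44 ≈ 36, which caps the further loss at 6.

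**Overlap among the unnamed exclusions.**

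- Low TSH is one of the triggers for dose reduction in Protocol 7.4.3, so subjects reduced for that reason have already failed the TSH condition.
- A subject out of range earlier may also be out of range at the end or stop early, and both of those reasons are already named.
- Non-primary disease may be rare or absent. Protocol 5.1 puts secondary disease down mostly to pituitary tumor or trauma, exclusion criterion 25 removes many such histories, and SAP 9.5 provides for the case where every subject has primary disease.

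The losses therefore do not add up, and their total cannot be derived.

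**The case for a change.** The strongest case for acting is that this is the test that sets the sample size, and the stated reasons for 44 do not describe the set that is tested. The plan reports the two TSH counts separately, so the difference is more than loose phrasing. The seven sensitivity analyses in SAP 9.5 bring back subjects with dose changes or other diagnoses where applicable, but they do not restore power to the primary test. Correcting the sentence in three places would be cheap.

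The mismatch stands, and so does the remark that the reader cannot tell what qualifying rate was assumed. The claim that 44 is too few does not stand. It holds only if the 6 spare subjects were computed from end-of-study losses and nothing else, and neither document says so. A corrected sentence would need a qualifying rate that only the sponsor can supply. A printed power table would have to pick between SD 0.459 and 0.472, a choice the plan does not make. Whether the Day 1 predose TSH counts towards the whole-period condition is a definition that analysts can settle when they program the set.

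**Conclusion.** The justification for 44 is worded more narrowly than the primary analysis set, but no stated figure fails. The 38 reproduces under either reading of the correlation, and 44 allows a total loss of 13.6%. Whether that is enough cannot be decided from the documents, because every shortfall figure rests on an assumed rate.

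If the number qualifying falls to between 30 and 36, power is 0.66 to 0.78 at SD 0.459, or 0.62 to 0.74 at SD 0.472. A smaller true SD would soften this: with 26 subjects, power is 0.76 at SD 0.393 and 0.96 at SD 0.30.

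Fewer subjects cost precision, not validity. SAP 9.5 reports a geometric mean ratio with a 90% interval, and both remain valid at whatever number qualifies. At SD 0.459 the interval runs from the estimate divided by, to the estimate multiplied by, exp(1.687 × 0.459/√38) = 1.13 with 38 subjects, and exp(1.699 × 0.459/√30) = 1.15 with 30. Rewording the sentence would alter no analysis set, model or result, and the documents give no basis for enrolling more. No change to the plan follows.

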### 13.2. Subject Disposition

The number of subjects enrolled, included in each analysis population, who complete the study, and who prematurely discontinue, along with reason for discontinuation will be summarized.

### 13.3. Demographic and Baseline Characteristics

Demographic and baseline characteristics will be summarized for all subjects. Summary statistics will be generated for continuous variables and the number and percentage of subjects within each category will be presented for categorical variables.

### 13.4. Analysis Populations

**Safety Population:** All subjects who receive at least 1 dose of XP-8121.

**Completer Population:** All subjects who complete the Maintenance Period and exhibit normalized TSH throughout the Maintenance Period while on a stable dose for approximately 6 weeks.

**PK Population:** All safety population subjects who participate in the PK substudy, who do not have any major protocol deviations affecting the PK endpoints and for whom a sufficient number of samples is available to determine at least one PK parameter.

## 13.5. Study Endpoints

### 13.5.1. Primary Endpoints

- Safety endpoints collectively include incidence, frequency, severity, and relationship to study drug of TEAEs, including clinically significant vital sign measurements, safety laboratory test results, ECGs, and physical examinations
- Tolerability assessments include Modified Draize Scale and Injection Site Discomfort questionnaires
- Geometric mean ratio of the weekly dose of XP-8121 SC (in  $\mu\text{g}$ ) to the daily dose of oral levothyroxine (aka dose conversion factor), where the XP-8121 dose corresponds to the administration immediately preceding collection of blood TSH used to determine normalization at the end of Maintenance Period

#### 13.5.1.1. Analysis of Primary Endpoint (Dose Conversion Factor)

The final dose conversion factor will be assessed by comparing the ln-transformed final XP-8121 SC dose (in  $\mu\text{g}$ ) that maintains normalized TSH throughout the Maintenance Period to the ln-transformed daily oral levothyroxine dose (in  $\mu\text{g}$ ) the subject was taking before the study, using a linear mixed effects model with treatment as fixed effects, and subject as random effect. Geometric LSMEs, geometric mean ratios, and 90% CIs will be presented. This endpoint will be analyzed using the Completer population for subjects with primary hypothyroidism only. Additional sensitivity analyses that include subjects with secondary/tertiary hypothyroidism, subjects with dose adjustment, and/or subjects that maintain normal free T4 may be conducted. The details of the sensitivity analyses will be described in the SAP.

Analysis of safety endpoints will be described in Section 13.7.

### 13.5.2. Secondary Endpoints

The secondary endpoints of the study are as follows:

- Proportion of subjects enrolled with normalized TSH throughout the Maintenance Period
- Proportion of subjects enrolled with normalized TSH at the end of Maintenance Period
- Blood thyroid hormone concentrations (total thyroxine, fT4 and TSH) following the first dose of XP-8121 and after titration (ie, during the Titration and Maintenance Periods)

#### 13.5.2.1. Analysis of Secondary Endpoints

Secondary endpoints will be analyzed for the safety population, for subjects with primary hypothyroidism only and for all subjects, if applicable. Subjects with normalized TSH throughout the Maintenance Period and at the end of Maintenance Period will be presented by number and percentage of subjects referenced to the safety population and the number of subjects entering the Maintenance Period, along with corresponding 95% CIs. TSH, total and free T4 measures following the first dose of XP-8121 will be summarized using descriptive statistics. Number and percentage of subjects with results outside the normal ranges will be tabulated.

### 13.5.3. Exploratory Endpoints

- Observed values and changes from baseline values in thyroid hormones (total and fT4) and TSH during the Titration and Maintenance Periods
- Pharmacokinetic profile of plasma thyroid hormones (T4 and T3 during the 168-hr PK period (PK substudy only):
  - $T_{max}$
  - $C_{max}$  and  $C_{max}$  normalized by dose ( $C_{max}/Dose$ )
  - $AUC_{0-168hr}$  and  $AUC_{0-168hr}$  normalized by dose ( $AUC_{0-168hr}/Dose$ )
  - If supported by the data, the following additional parameters may be calculated:
    - Total apparent clearance (CL/F)
- Comparison of the score of Convenience, Overall Satisfaction, and Effectiveness domain of the TSQM-9 between oral levothyroxine and once-weekly XP-8121 SC treatments
- Summary of results from the Subject Preference Survey

#### 13.5.3.1. Analysis of Exploratory Endpoints

All exploratory endpoints except for PK endpoints will be analyzed for the safety population, for subjects with primary hypothyroidism only and for all subjects, if applicable. TSH, total and free T4 measures and changes from baseline will be summarized by each protocol-specified timepoint using descriptive statistics. Analysis of PK endpoints will be described in Section 13.6.

The analysis of the exploratory endpoint of TSQM-9 domain scores will be gated on results from the primary endpoint analysis. The three domain scores will be hierarchically analyzed to ensure control of the family-wise type I error rate at the 0.05 level, with the Convenience score first, Overall Satisfaction score second, and Effectiveness third. Hypothesis tests for the three domain scores will be based on null hypotheses that assume no difference between oral levothyroxine and once-weekly XP-8121 SC treatments. Each domain score will be compared between the two treatments using a paired t-test.

Subject counts and percentages for each answer to each question from the Subject Preference Survey will also be presented.

## 13.6. Pharmacokinetics

Plasma PK parameters will be summarized for all subjects in the PK Population, using descriptive statistics (number of non-missing observations (N), arithmetic mean, SD, CV%, median, minimum, maximum, geometric mean, and geometric CV%).

Total plasma concentration of thyroxine and triiodothyronine will be summarized by collection timepoint within the PK period for all subjects in the PK Population using descriptive statistics (N, arithmetic mean, SD, CV%, median, minimum, maximum, geometric mean, and geometric CV%).

## 13.7. Safety and Tolerability

All safety analyses will be performed using the Safety population. Safety data will be collected and summarized by study period (Titration Period, Maintenance Period). No formal hypotheses will be tested on safety data.

### 13.7.1. Adverse Events

Adverse events will be coded using the Medical Dictionary for Regulatory Activities (MedDRA) version 25.0 or higher. Listings of all AEs, treatment-emergent SAEs, and TEAEs leading to study discontinuation will be provided by subject, study period, verbatim term, MedDRA System Organ Classification (SOC) and Preferred Term (PT), start and end dates, seriousness, severity, relationship to study drug, action taken with study treatment, and outcome.

AEs will be summarized overall by the number and percentage of subjects who experienced at least one AE of the following categories in each study period: any AE, any TEAE, any drug-related TEAE, any severe TEAE, any serious TEAEs, any drug-related SAE, any SAE leading to death, any TEAE leading to premature discontinuation of study drug, and any SAE leading to premature study drug discontinuation.

The number and percentage of subjects reporting a TEAE in each study period and overall (while taking XP-8121) will be tabulated by SOC and PT; by SOC, PT, and severity (mild, moderate, and severe); and by SOC, PT, and relationship to study drug.

The number and percentage of subjects reporting an SAE or reporting a TEAE leading to premature discontinuation of study drug in each study period and overall will be summarized by SOC and PT.

### 13.7.2. Laboratory Evaluations, Vital Sign Measurements, and Electrocardiograms

Laboratory evaluations (including TSH), vital signs, and ECG assessments will be summarized by study period, and protocol-specified collection timepoint within each period using descriptive statistics. A summary of change from baseline at each protocol-specified timepoint will also be presented.

Listings of clinically significant abnormal laboratory values will be presented. Individual laboratory results will be listed indicating values outside normal range. Vital signs and electrocardiogram results will be listed.

### 13.7.3. Prior and Concomitant Medications

Prior and concomitant medications will be mapped to a World Health Organization (WHO) drug classification using WHO Drug Dictionary (WHO-DD) and summarized for anatomical therapeutic chemical (ATC), and PT.

Prior and concomitant medication will be summarized for all subjects. A listing of prior and concomitant medications will be provided for the safety population.

